#### **12.2.1 Safety Analysis Set**

The safety analysis set is defined as the population consisting of subjects who are enrolled in the study, excluding “those who have not received the study drug.”

#### **12.2.2 Efficacy Analysis Set**

The full analysis set (FAS) is defined as the population consisting of subjects who are enrolled in the study, excluding the following subjects:

- 1) Subjects who have not received the study drug
- 2) Subjects who have not undergone efficacy evaluation even once

#### **12.2.3 Pharmacokinetic Analysis Set**

The pharmacokinetic analysis set is defined as the population consisting of subjects who are enrolled in the study and have received the investigational drug and also meet all of the criteria listed below. However, subjects receiving placebo will be excluded:

- 1) Receiving the investigational drug as specified in the protocol

- 2) Having no major protocol violations (eg, violation of the inclusion/exclusion criteria)
- 3) Having plasma drug concentration data collected and available for at least 1 time point

#### **12.2.4 Pharmacodynamic Analysis Set**

The pharmacodynamic analysis set is defined as the population consisting of subjects who are enrolled in the study and meet all of the following criteria:

- 1) Receiving the investigational drug as specified in the protocol
- 2) Having no major protocol violation (eg, violation of the inclusion/exclusion criteria)
- 3) Having pharmacodynamic data collected and available for at least 1 time point

### **12.3 Statistical Analysis**

#### **12.3.1 Efficacy Analyses**

##### **12.3.1.1 Primary Efficacy Analyses**

- 1) Summary statistics of the NIHSS score at each assessment point will be calculated by treatment group. Summary statistics of the change in the NIHSS score at each assessment point relative to baseline will be calculated by treatment group.
- 2) The frequency of the mRS score at each assessment point will be tabulated by treatment group. The proportion of subjects with good prognosis based on the mRS score (mRS score of 0 to 2) on Days 30 and 90 will be calculated by treatment group.

##### **12.3.1.2 Secondary Efficacy Analyses**

Not applicable.

##### **12.3.1.3 Exploratory Efficacy Analyses**

The frequency of the TICI grade will be tabulated by treatment group.

In addition, the proportion of subjects achieving TICI 3 immediately after thrombectomy device treatment will be calculated by treatment group.

#### **12.3.2 Pharmacokinetic/Pharmacodynamic Analyses**

##### **12.3.2.1 Pharmacokinetic Analyses**

Summary statistics of plasma concentrations and pharmacokinetic parameters will be calculated by treatment group. In addition, changes in plasma concentrations over time will be graphically displayed.

Results of modeling and simulation (M&S), including population pharmacokinetics and pharmacokinetic/pharmacodynamic analyses, if performed, will be separately reported.

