**Table 5.1-1 Dose Level and Predicted Blood Concentrations for Each Cohort**

Cohort	Dose (mg)	Preparation		Infusion Rate for the Loading Dose (30-minute Intravenous Infusion of 25% of the Entire Amount)	Infusion Rate for the Maintenance Dose (5.5-hour Intravenous Infusion of 75% of the Entire Amount)	CLcr (mL/min)	Predictive Value Obtained Using Data from the Single-dose Study in Healthy Subjects			
		Drug Solution Volume (mL)	0.9% Saline (mL)				C 0.5h (ng/mL)	C max (ng/mL)	T max (h)	AUC (ng·h/mL)
1	0.6	0.6	100	0.84 mL/min	0.23 mL/min	60	14.3	15.8	6	144
							90	13.9	0.5	118
							120	13.6	0.5	100
2	1.2	1.2	100	0.84 mL/min	0.23 mL/min	60	28.6	31.7	6	288
							90	27.9	0.5	236
							120	27.2	0.5	200
3	2.4	2.4	100	0.85 mL/min	0.23 mL/min	60	57.2	63.4	6	576
							90	55.8	0.5	472
							120	54.5	0.5	400
4	4.8	4.8	100	0.87 mL/min	0.24 mL/min	60	114	127	6	1151
							90	112	0.5	944
							120	109	0.5	800

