#### <Rationale>

In Study DS1040-A-U101 in healthy subjects, the IC90 value in clot lysis assay was reported to be 38.2 ng/mL. Based on the results of modeling and simulation (M&S) constructed using data from the single-dose study in healthy subjects (DS1040-A-U101), the Cmax value in subjects with body weight of 60 kg was predicted to be 23.8 ng/mL to 31.7 ng/mL for Cohort 2 (DS-1040b 1.2 mg), indicating that the dose level in Cohort 2 is

expected to provide increased endogenous fibrinolytic activity. Due to the lack of clinical experience with DS-1040b in Japanese patients with acute ischemic stroke in whom a thrombectomy device is indicated, the dose level in Cohort 1 (DS-1040b 0.6 mg) will be used as a starting dose to confirm the safety of DS-1040b in this study.

In the drug-drug interaction study with aspirin (DS1040-A-E102), Cmax and AUC of DS-1040a following 6-hour intravenous infusion of DS-1040b 6 mg were 582 ng/mL and 1118 h·ng/mL, respectively, indicating that DS-1040b does not increase the prolongation of bleeding associated with aspirin under these conditions. In the drug-drug interaction study with clopidogrel (DS1040-A-E106), Cmax and AUC of DS-1040a following 12-hour intravenous infusion of DS-1040b 20 mg were 290 ng/mL and 3670 h·ng/mL, respectively, indicating that DS-1040b does not increase the prolongation of bleeding associated with clopidogrel under these conditions. In the drug-drug interaction study with enoxaparin (DS1040-A-U104), Cmax and AUC of DS-1040a following 12-hour intravenous infusion of DS-1040b 20 mg were 304 ng/mL and 4079 h·ng/mL, respectively, confirming the safety and tolerability of DS-1040b.

Cmax and AUC in Cohort 4 (DS-1040b 4.8 mg) were predicted to be 95.3 ng/mL to 127 ng/mL and 800 h·ng/mL to 1151 h·ng/mL, respectively, suggesting that the dose level in Cohort 4 may also be associated with a low bleeding risk. Thus, doses ranging from 0.6 mg to 4.8 mg will be used in this study.

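### The committed PK analysis is by dose only, although exposure is predicted by creatinine clearance; chance imbalance in CLcr could shift between-dose AUC ratios by roughly 10–20%

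*Combined protocol and SAP*

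**What the plan says.** Section 12.3.2.1 sets out the pharmacokinetic analysis: "Summary statistics of plasma concentrations and pharmacokinetic parameters will be calculated by treatment group". It adds graphs of concentration over time. Modelling is mentioned but left open: "Results of modeling and simulation (M&S), including population pharmacokinetics and pharmacokinetic/pharmacodynamic analyses, if performed, will be separately reported". No covariate, renal-function grouping or dose normalisation is named. Section 12.1 leaves more specific methods to a separate SAP, whose PK content is not in the text available.

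The dose rationale is built differently. Table 5.1-1, under the heading "Predictive Value Obtained Using Data from the Single-dose Study in Healthy Subjects", gives a row for each of CLcr 60, 90 and 120 mL/min at every dose. For 0.6 mg, the first and last rows read "60 14.3 15.8 6 144" and "120 13.6 0.5 100" (the last figure in each is AUC). For the top dose, the rationale in Section 5.1.1 restates the tabulated AUC as a range, 800 to 1151 h·ng/mL, and draws a safety inference from the predicted exposure: "suggesting that the dose level in Cohort 4 may also be associated with a low bleeding risk".

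Plasma and urine pharmacokinetics are a named secondary endpoint.

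**The concern.** The protocol treats renal function as a main driver of exposure. Section 1.2.1.6 reports lower total and renal clearance in healthy elderly subjects and links the longer half-life to the renal part. A prediction made by CLcr is best checked by CLcr, but the committed analysis pools all renal function within a dose.

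Randomisation does not help here. It allocates DS-1040b against placebo within Cohorts 2 to 4, and placebo subjects are outside the PK analysis set (Section 12.2.3). Comparisons between doses are therefore comparisons between successive small groups, recruited within a study period running from April 2017 to June 2020. The synopsis lists no stratification factors. The rule on subjects aged 81 or over makes some elderly subjects likely in each cohort, but it does not fix the age mix. Ages run to 89, and renal eligibility is a serum creatinine limit (exclusion at 2 mg/dL or more), with no CLcr floor.

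At stake is how clearly a secondary endpoint can be read: whether exposure rises in proportion to dose, and whether it agrees with Table 5.1-1 in this population.

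**Working it through.** **Inputs.** Predicted AUC by dose and CLcr (Table 5.1-1); active subjects per dose, 6 or 12 at 0.6 mg and 12 at each higher dose (Section 12.5); clearance in healthy subjects (Section 1.2.1.6). The CLcr spread in this population is not given, so two spreads are assumed.

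**1. The plan's own figure.**

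| Dose (mg) | AUC at CLcr 60 / 90 / 120 (ng·h/mL) | Ratio 60 : 120 |
|---|---|---|
| 0.6 | 144 / 118 / 100 | 1.44 |
| 1.2 | 288 / 236 / 200 | 1.44 |
| 2.4 | 576 / 472 / 400 | 1.44 |
| 4.8 | 1151 / 944 / 800 | 1.439 |

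**2. Implied clearance.** CL = dose/AUC gives 600/144 = 4.17, 600/118 = 5.08 and 600/100 = 6.00 L/h. A line through the outer points has slope (6.00 − 4.167)/60 = 0.03056 and intercept 6.00 − 0.03056 × 120 = 2.333. At CLcr 90 it returns an AUC of 118.0, against 118 in the table. Reported mean clearance at the matched 3 and 6 mg doses was 4.06–5.37 L/h in elderly and 6.04–6.24 L/h in non-elderly subjects. At 0.6 mg that gives AUC of 600/6.24 = 96 to 600/4.06 = 148, which brackets the tabulated 100–144.

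**3. Do adjacent doses overlap?** Over CLcr 60–120 the predicted ranges are 100–144, 200–288, 400–576 and 800–1151. The gap factor is 200/144 = 1.39. Even at CLcr 30, extrapolating the line, AUC at 0.6 mg is 600/(2.333 + 0.03056 × 30) = 185, still below 200. In the extreme case of one group all at CLcr 60 and the other all at 120, a true doubling would appear as 2 × 100/144 = 1.39 or 2 × 1.44 = 2.88.

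**4. Chance imbalance.** Assume CLcr uniform over a range, CL from the line above, and no other variability. The SD of ln AUC is then 0.105 (60–120) or 0.175 (30–120). The upper 95% limit for the ratio of geometric means is approximately exp(1.96 × SD × √(1/n₁ + 1/n₂)). Simulating 200,000 group pairs gives the ranges in the fourth column.

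| CLcr range | Group sizes | Formula | Simulated 95% range | A true doubling appears as |
|---|---|---|---|---|
| 60–120 | 6 v 12 | 1.11 | 0.90–1.11 | 1.80–2.22 |
| 60–120 | 12 v 12 | 1.09 | 0.92–1.09 | 1.84–2.17 |
| 30–120 | 6 v 12 | 1.19 | 0.84–1.18 | 1.68–2.37 |
| 30–120 | 12 v 12 | 1.15 | 0.87–1.15 | 1.74–2.30 |

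**5. What adjustment gains.** Add an assumed residual CV of 20% or 30%. For 12 v 12, the 95% half-width factor falls from 1.20–1.24 to 1.17 (CV 20%), or from 1.28–1.32 to 1.26 (CV 30%). The gain in precision is modest. The larger gain is that each observation can be set against the prediction for its own renal function.

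**6. CLcr below the table.** The documents name no CLcr formula. Taking Cockcroft-Gault as an assumption, a man aged 85 weighing 60 kg with creatinine 1.0 mg/dL has (140 − 85) × 60/(72 × 1.0) = 46 mL/min. With creatinine 1.9 it is 24; at age 75, 60 kg and 0.9 it is 60. So eligible subjects can fall outside the tabulated 60–120. At 46 mL/min the extrapolated AUC for 4.8 mg is 4800/(2.333 + 0.03056 × 46), about 1280, above the tabulated maximum of 1151.

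**The case against.** The best defence is that the PK objective is only to measure concentrations and calculate parameters. No hypothesis is stated, and confirming Table 5.1-1 or dose proportionality is not a declared aim. Escalation under Section 12.4 turns on bleeding, organ impairment and treatment-related SAEs, not on exposure. Detail is deferred to the SAP. Because the ingredients of CLcr are collected, the analysis could be run later. The safety argument also has room: AUCs in the clopidogrel and enoxaparin studies were 3670 and 4079 h·ng/mL, or 3.2 and 3.5 times 1151.

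Most of this stands, and it limits how much weight the point can carry. It does not answer why a renal driver built into the dose rationale is absent from the committed analysis. An analysis added after the data are seen is also worth less than one named in advance.

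A reader might go further in three ways that the documents do not support:

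- That the dose groups cannot be compared with each other or with Table 5.1-1. Doses double, the predicted ranges do not overlap, and a group mean can be set beside the predicted range, as Section 5.1.1 itself does.
- That renal clearance of the drug, summarised by dose, is uninterpretable. Nothing shows this. Section 9.1 plans CLr and urinary excretion, so high AUC with low CLr would already point to renal function.
- That no covariate analysis is foreseen. Population PK is foreseen; it is just not committed.

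**Conclusion.** The point holds in a limited form. The protocol predicts a 44% higher AUC at CLcr 60 than at 120 mL/min but commits to no analysis that uses CLcr. With 6 to 12 active subjects per dose, sequential unstratified cohorts and no CLcr floor, imbalance in renal function could shift a between-dose AUC ratio by roughly 10% (CLcr 60–120) to 20% (CLcr 30–120). Dose proportionality is blurred; a doubling is not hidden.

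These sizes rest on assumed uniform CLcr spreads, on the line implied by Table 5.1-1 (extrapolated below 60) and on chance alone; a drift in case mix between cohorts could add to them. The point concerns a secondary endpoint and bears on no escalation decision. It is an inexpensive improvement, not a threat to the primary safety analysis.

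**What to change.** In Section 12.3.2.1 or the SAP:

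1. Derive baseline CLcr by a named formula from predose creatinine, age, sex and body weight. Sections 6.1 and 6.11 allow weight to be recorded late, up to Visit 4, so state how a late or missing weight is handled.
2. In the PK analysis set (at most 6 + 36 = 42 or 12 + 36 = 48 active subjects), list and plot individual CLr and dose-normalised AUC and Cmax against CLcr. Overlay the Table 5.1-1 predictions and flag CLcr outside 60–120.
3. Before comparing, state how the planned AUClast corresponds to the table's AUC, which has no stated time limit. Check the Cmax predictions too: the rationale gives 95.3–127 ng/mL at 4.8 mg, while the table as read here appears to give 109–127. The table's columns are broken in this text, so check the original.
4. Fit one model of log exposure on log dose and CLcr. Report geometric means by dose at a common CLcr with 95% confidence intervals, beside the planned by-dose summaries.

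Alternatively, make population PK with CLcr as a covariate a committed analysis.

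The cost is SAP wording, one derived variable, a table and a figure, with slightly more analysis work and no new data.

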#### **12.3.2.2 Pharmacodynamic Analyses**

Summary statistics of pharmacodynamics parameters (D-dimer level, TAFIa activity, and TAFI antigen level) will be calculated by treatment group. In addition, changes in each pharmacodynamic parameter over time will be graphically displayed.

#### **12.3.2.3 Biomarker Analyses**

Not applicable.

#### **12.3.2.4 Pharmacogenomic Analyses**

Not applicable.

### **12.3.3 Safety Analyses**

#### **12.3.3.1 Analysis of Primary Endpoints**

The point estimate and 95% confidence interval of each endpoint listed below will be estimated. Data from the placebo groups of all cohorts will be integrated, whereas data from the DS-1040b groups will be summarized by dose.

- 1) Incidence of symptomatic intracranial hemorrhage (defined by ECASS) within 36 hours after the start of study drug administration
- 2) Incidence of asymptomatic intracranial hemorrhage within 36 hours after the start of study drug administration
- 3) Incidence of non-intracranial (TIMI) major bleeding within 96 hours after the start of study drug administration

#### **12.3.3.2 Adverse Event Analyses**

The incidence of treatment-emergent adverse events (TEAEs) will be calculated by treatment group, and the frequency of each TEAE will be tabulated by event and by severity. Similar analyses will be performed for treatment-related and bleeding TEAEs.

A TEAE is defined as an AE that is not present prior to the study and occurs after the start of study drug administration but before Visit 5 (Day 30), or an AE that worsens in severity after the start of study drug administration but before Visit 5 (Day 30).

#### **12.3.3.3 Clinical Laboratory Evaluation Analyses**

Shift tables for the determination of normal and abnormal values will be prepared.

Summary statistics of hematology and blood chemistry data at each time point will be calculated by treatment group, and the change at each time point from baseline will be graphically displayed.

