### 4.2 Exclusion Criteria

Subjects who meet any of the following criteria will be disqualified from entering the

study:

- 1) Having received or planned to receive treatment with a thrombolytic drug (ie, urokinase or rt-PAs)
- 2) Having Intracranial or subarachnoid hemorrhage confirmed by head imaging (computed tomography [CT] or magnetic resonance imaging [MRI])
- 3) Having experienced a suspected bleeding event, such as gastrointestinal hemorrhage
- 4) Having a history of intracranial hemorrhage or a cerebral hemorrhage risk such as intracranial tumor, cerebral aneurysm, and cerebral arteriovenous malformation
- 5) Having a complication of aortic dissection
- 6) Having a history of serious head/spinal cord injury or surgery within 3 months
- 7) Having a history of gastrointestinal or urinary tract hemorrhage within 21 days
- 8) Having undergone a major surgery or experienced serious non-head injury within 14 days
- 9) Having activated partial thromboplastin time (aPTT) or partial thromboplastin time (PTT) of  $> 2$  times the normal value
- 10) Having an international normalized ratio (INR) of  $> 1.7$
- 11) Having a platelet count of  $< 100,000/\text{mm}^3$
- 12) Having uncontrolled hypertension despite drug therapy (systolic  $> 185 \text{ mmHg}$  and diastolic  $> 110 \text{ mmHg}$ )
- 13) Having a baseline blood glucose level of  $> 400 \text{ mg/dL}$
- 14) Having occlusion of at least two major arteries
- 15) Treatment with a stent-type thrombectomy device is not indicated due to the presence of carotid artery dissection, occlusion/vasculitis of the entire carotid artery/neck, contrast media allergy, etc.
- 16) Having a severe hepatic disorder (fulminant hepatitis, hepatic cirrhosis, hepatic tumor, or other hepatic disorders meeting any of the following criteria)

Parameter	Criterion
Total bilirubin	$\geq 3.0 \text{ mg/dL}$
AST (GOT)	$\geq 2.5 \times$ the upper limit of reference range or $\geq 100 \text{ U/L}$
ALT (GPT)	$\geq 2.5 \times$ the upper limit of reference range or $\geq 100 \text{ U/L}$
ALP	$\geq 2.5 \times$ the upper limit of reference range

- 17) Being on chronic dialysis or having a severe renal disorder (eg, nephrotic syndrome, acute/chronic renal failure, uremia, and hydronephrosis) or a serum creatinine level of  $\geq 2 \text{ mg/dL}$ .
- 18) Having a history of ischemic stroke within 30 days prior to the study drug

administration

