## **6.14 Electrocardiogram**

Findings of 12-lead ECG obtained before the start of study drug administration and at Visit 2 will be assessed as “normal,” “abnormal, not clinically significant,” or “clinically

significant.” The assessment and the date/time of measurement will be recorded in the CRF. If assessed as “clinically significant, it should be determined whether the finding is regarded as an AE. Findings that have already been noted prior to study drug administration and have not worsened after study drug administration will not be regarded as AEs. For findings regarded as AEs, the event will be recorded in the CRF.

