## **6.15 Laboratory Tests**

The parameters listed below will be measured before and at 6 hours after the start of study drug administration, at Visits 2 and 4, and at the time of discontinuation, and the presence or absence of measurements, the date/time of blood collection, and the measurement results will be recorded in the CRF. Each study center’s reference ranges will be used for laboratory data.

- Hematology test: red blood cell count, hemoglobin, hematocrit, white blood cell count, white blood cell differential (neutrophil, lymphocyte, monocyte, eosinophil, basophil), platelet count
- Blood chemistry test: total protein, albumin, A/G ratio, total bilirubin, direct bilirubin, AST, ALT, ALP,  $\gamma$ -GT, LDH, CK, BUN, creatinine, uric acid, Na, K, Cl, Ca, P, Mg, total cholesterol, triglyceride, glucose, CRP

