## **10.3 Adverse Events of Special Interest**

### **10.3.1 Combined Elevations of Aminotransferases and Bilirubin**

Combined elevations of aminotransferases and bilirubin, either serious or non-serious, and independent of causal relationship, meeting the laboratory criteria for a potential case of Hy's Law (ALT or AST  $\geq$  3 times the upper limit of normal [ULN] with simultaneous TBL  $\geq$  2 times the ULN) should always be reported to the sponsor using the CRF, with the investigator's or subinvestigator's assessment of seriousness, causality, and a detailed narrative. These events should be reported within 24 hours of the investigator or subinvestigator becoming aware of the event (for the procedures for reporting, refer to Section 10.5).

If the subject discontinues study drug due to liver enzyme abnormalities, the subject will have additional clinical and laboratory evaluations as described in "Section 5.7 Subject Withdrawal/Discontinuation" in order to determine the nature and severity of the potential liver injury.

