#### **12.3.3.5 Electrocardiogram Analyses**

A frequency table of investigator-assessed 12-lead ECG data at each measurement point will be prepared.

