#### **12.4.2 Criteria for Discontinuation or Temporary Discontinuation of the Study**

If any of the criteria specified below are met, the study will be discontinued or temporarily discontinued. Similarly, the study may be discontinued or temporarily discontinued according to these criteria until 3 subjects aged  $\geq 81$  years are enrolled in the DS-1040b group in each cohort.

- 1) If the criterion below is met, the study will be discontinued at that point. After the decision on discontinuation is made, the sponsor will discontinue the study according to the procedures described in Section 16.9:
  - Occurrence of two events of symptomatic intracranial hemorrhage (intracranial hemorrhage with clinical deterioration causing an increase in the NIISS score of  $\geq 4$  points [defined by ECASS]) not attributable to external factors at 36 hours after the start of DS-1040b administration in the DS-1040b group in one cohort
- 2) To ensure the safety of subjects, subject enrollment will be temporarily discontinued and the necessary actions to be taken, including discontinuation of the study, will be considered if any of the criteria listed below are met. If the study is continued based on the results of consideration, subject enrollment will be resumed. If the study is discontinued, the sponsor will discontinue the study according to the procedures described in Section 16.9:
  - Occurrence of one event of symptomatic intracranial hemorrhage (intracranial hemorrhage with clinical deterioration causing an increase in the NIHSS score of  $\geq 4$  points [defined by ECASS]) not attributable to external factors at 96 hours after the start of study drug administration (Visit 4) in the DS-1040b group in one cohort
  - Occurrence of one event of non-intracranial (TIMI) major bleeding at 96 hours after the start of study drug administration (Visit 4) in the DS-1040b group in one cohort
  - Occurrence of any events requiring the consideration of study discontinuation, such as severe hepatic impairment (eg, total bilirubin  $\geq 10$  mg/dL, AST or ALT  $\geq 500$  IU/L, ALP of 5 times the study center’s reference range, bleeding tendency, symptoms of hepatic failure, including consciousness disorder [fulminant hepatitis], hepatic cirrhosis, hepatic tumor, jaundice persisting for

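### The final safety tables cannot show laboratory worsening in subjects who enter with abnormal values, nor how many subjects changed ECG grade

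*Combined protocol and SAP*

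**What the plan says.** Section 12.3.3.3 gives the categorical laboratory display in one sentence: "Shift tables for the determination of normal and abnormal values will be prepared". It then adds "Summary statistics of hematology and blood chemistry data at each time point will be calculated by treatment group", with a graph of change from baseline. Section 6.15 decides what counts as normal: each center's own "reference ranges will be used for laboratory data".

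For the ECG, Section 12.3.3.5 says "A frequency table of investigator-assessed 12-lead ECG data at each measurement point will be prepared". Section 6.14 provides three investigator grades (normal; abnormal but not clinically significant; clinically significant), recorded before dosing and at Visit 2.

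Three other sections set numerical limits on laboratory values:

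- **Section 4.2 (entry).** The hepatic exclusion covers "fulminant hepatitis, hepatic cirrhosis, hepatic tumor, or other hepatic disorders meeting any of the following criteria", and the criteria are AST or ALT at 2.5 times the upper limit or 100 U/L, ALP at 2.5 times the upper limit, and total bilirubin at 3.0 mg/dL. Creatinine excludes at 2 mg/dL. Values below these limits may enter even if they lie outside the reference range. BUN and potassium have no entry limit.
- **Section 12.4.2 (temporary discontinuation).** One criterion is "Occurrence of any events requiring the consideration of study discontinuation, such as severe hepatic impairment". Its examples include bilirubin of 10 mg/dL, AST or ALT of 500 IU/L, ALP at 5 times the reference range, creatinine of 4 mg/dL, BUN of 40 mg/dL and potassium of 5.5 mEq/L.
- **Section 10.3.1 (special interest).** "Combined elevations of aminotransferases and bilirubin, either serious or non-serious, and independent of causal relationship" must be reported when ALT or AST is at least 3 times, and bilirubin at least 2 times, the upper limit.

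Section 12.3.3 plans no graded shift, no worst post-dose value and no count of subjects crossing any of these limits.

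**The concern.** Safety and tolerability are the primary objective, and each dose group has 6 or 12 treated subjects. In groups that small, a signal is likely to be one or two individuals, so a useful table shows where each subject started and how far that subject moved. A normal/abnormal shift table does this only for subjects who start normal. The entry limits leave a range of abnormal but eligible values, and the Section 12.4.2 values lie well above that range. A subject can cross the whole distance without leaving the abnormal category.

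The ECG display has a related fault. Separate counts at two times give the totals but not the transitions, so balanced counts may hide subjects who worsened behind others who improved.

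What is at stake is the final report: someone comparing doses from these tables could see no shift where a subject had deteriorated markedly.

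**Working it through.** The plan states no figure on this point, so there is none to reproduce. The check is of what the planned tables can show.

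**1. Laboratory shift.** Inputs are the entry limits (Section 4.2) and the example values in Section 12.4.2. The documents give no numerical upper limits of normal, because each center uses its own, so these are assumptions shown as ranges. A shift is recorded only if exactly one of the two values is above the upper limit.

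| Parameter | Assumed upper limit | Entry limit | Predose | Post-dose | 12.4.2 value | Planned table |
|---|---|---|---|---|---|---|
| Creatinine, mg/dL | 1.0 to 1.2 | below 2 | 1.5 | 4.2 | 4 | abnormal to abnormal |
| Creatinine, mg/dL | 1.0 to 1.2 | below 2 | 0.9 | 4.2 | 4 | normal to abnormal |
| ALT, U/L | 40 | below 100 (2.5 × 40 = 100) | 70 | 520 | 500 | abnormal to abnormal |
| AST, U/L | 30 to 40 | below 75 to 100 (2.5 × 30 = 75) | 70 | 500 | 500 | abnormal to abnormal |
| Bilirubin, mg/dL | 1.2 to 1.5 | below 3.0 | 2.9 | 10 | 10 | abnormal to abnormal |

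The two creatinine rows end at the same value. Only the subject who began normal appears as a shift. The result does not change anywhere in the assumed ranges.

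**2. Do the group summaries make up for it?** If one subject changes and the others do not, the mean change is (post-dose − predose)/n.

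- Creatinine 1.5 to 4.2: 2.7/12 = 0.225 mg/dL, or 2.7/6 = 0.45 mg/dL.
- ALT 70 to 520: 450/12 = 37.5 U/L, or 450/6 = 75 U/L.

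A mean does not separate one large rise from small rises in everyone. A maximum, if reported, would reveal the extreme value but not that subject's predose value.

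**3. ECG.** Take 12 subjects, 6 abnormal predose and 6 abnormal at Visit 2. Let x be the number going from normal to abnormal. The Visit 2 total stays at 6 only if x also go from abnormal to normal, so x can be any whole number from 0 to 6, with identical frequency tables. With three grades the same holds: from 6 normal, 4 abnormal but not clinically significant and 2 clinically significant, one subject moving from the second grade to the third and one moving back leaves 6, 4 and 2.

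**4. With the change.** In a table banded at 4 mg/dL, creatinine 1.5 to 4.2 moves from the band above the upper limit but under 4 to the band at or above 4. The ECG cross-tabulation gives x directly.

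**The case against.** The strongest reply is that these tables are not the safety system. Under Section 12.4.1 the sponsor obtains the safety data and reviews them with the medical expert before each escalation, and Section 12.4.2 acts on single events. A reader might infer that the tables would let a trial pause be missed. The documents do not support that, because the pause decision does not depend on the end-of-study tables. Section 12.4.2 also names no ECG threshold, so the comparison with pause values concerns laboratory data only.

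A reader might also infer that worsening surfaces only through an investigator who knows the allocation. That goes too far. Sections 10.3.1 and 10.5 require every combined aminotransferase and bilirubin elevation to be reported on fixed criteria within 24 hours, whatever its seriousness, and Section 10.3.1 adds whatever its cause. Section 6.14 requires each clinically significant ECG to be considered as an adverse event, and does not exempt findings that have worsened. Clinically evident bleeding with a hemoglobin fall of 5 g/dL or more is already a primary endpoint with blinded adjudication, so it needs no separate band here.

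A third inference is that a change from low to high is certain to be hidden. Section 12.3.3.3 does not say that low and high are merged; a low/normal/high layout is compatible with its wording. Nor does omitting the treatment group from the shift-table and ECG sentences show that pooled tables are intended.

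Finally, Section 12.1 calls its methods a summary and defers detail to a separate SAP, none of whose text is in the document reviewed. That SAP may specify more.

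All of this limits the consequence. It does not change what the stated tables can show: a low/normal/high layout would still record high to higher as no shift, and the ECG sentence specifies counts at each time point, not transitions.

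**Conclusion.** The point stands as a modest reporting weakness. As stated, the laboratory shift table cannot show worsening in a subject who enters with an eligible but abnormal value, and the ECG table cannot show how many subjects changed grade. The pause rule, the mandatory reports and the bleeding endpoints are unaffected, and the underlying values are recorded.

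The laboratory examples rest on assumed upper limits of normal (creatinine 1.0 to 1.2 mg/dL, AST 30 to 40 U/L, ALT 40 U/L, bilirubin 1.2 to 1.5 mg/dL). The ECG counts are hypothetical and show only what the table leaves open. How many subjects will enter with abnormal values cannot be judged from the documents. The conclusion also assumes that the separate SAP adds nothing to the two sentences; if it already specifies graded shifts and an ECG cross-tabulation, the point falls away.

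**What to change.** In Section 12.3.3.3, and in the SAP:

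- Present shift tables of predose against worst post-dose value, by dose and for pooled placebo. Use low/normal/high for all parameters, and say how the worst value is chosen where both directions matter.
- Add reporting bands at cut-offs the protocol already states: AST and ALT at 3 times the upper limit and 500 IU/L; bilirubin at 2 times the upper limit and 10 mg/dL; ALP at 2.5 and 5 times; creatinine at 2 and 4 mg/dL; BUN at 40 mg/dL; potassium at 5.5 mEq/L.
- Add a count, by group, of subjects meeting the Section 10.3.1 criteria.

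In Section 12.3.3.5, replace the frequency table with a predose-by-Visit 2 cross-tabulation of the three ECG grades by treatment group. Its margins still give the counts now planned.

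The bands are for display only and change no entry, pause or stopping rule. All the parameters are already collected under Sections 6.14 and 6.15. The cost is a few lines of wording and some extra, sparsely filled table rows.
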